7.1. RANDOM ASSIGNMENT TO DEVELOP STUDY GROUPS

If groups will be constructed by random assignment, please describe the process of random assignment and how random assignment will be monitored to prevent crossover of those assigned to specific study groups (e.g., individuals assigned to the comparison group who receive treatment) by addressing the questions below.

Who will conduct random assignment?	Eligible fathers who wish to participate in the study are randomly sorted into a treatment or control group by the CQI data manager or by case managers under supervision of the CQI Data Manager. The CQI Data Manager is trained by Senior staff and overseen by a Senior Consultant from MER.
When does random assignment occur (e.g., before or after enrollment)?	Orientation attendees who express interest in TCD services return the following week to enroll at their respective recruitment sites. Those who are also willing to participate in the impact study provide signed consent forms before they are assigned to study groups. After consent is documented, parents are randomly sorted into either a treatment or control group.
How and when are study participants informed of their assignment status?	Participants will be informed of their assignment status immediately after randomization.
Will groups be stratified in any way to ensure balance between treatment and control? If yes, what characteristics or methods will be used?	No.
What strategies will be used to ensure there is no re-assignment or non-random assignment to the treatment group?	A C2 (i.e., client profile) is entered onto nFORM to create a client profile for eligible parents who attend orientations for the TCD Project. Parents who return to participate in the study have their study group assignment entered onto nFORM. Only parents assigned to the treatment group as noted on nFORM can register and attend Ray of Hope workshops. Study group assignment cannot be changed once it has been noted on nFORM.

What strategies will be used to minimize crossovers?	The nFORM system produces an operational report that specifies study group assignment for all parents who agree to participate in the study. Study group assignment as noted on nFORM will be examined with the relevant operational report during CQI-Team meetings to make sure participants receive the services specific to their study group.
Who will be responsible for monitoring random assignment compliance?	The CQI Data Manager is responsible for monitoring random assignment compliance by case managers during study enrollment under the guidance of other CQI Team members. The distribution of participants across study groups will be monitored by the CQI Team using the relevant operational reports on nFORM.
What methods will be used to monitor the comparability of the study groups?	nFORM data will be used to produce enrollments into study groups to assess their comparability. Baseline equivalency analyses will determine whether there are statistically significant differences between study groups.

9. SAMPLE

9.1. TARGET POPULATION(S)

For each target population identified in Section 1.2, please describe the target population(s), and explicitly state whether the population(s) differs from those who will be broadly served by the grant. Describe how the target population will be identified. Explicitly state the unit of analysis (e.g., non-residential father, unmarried couple).

Description of Target Population	How is the population different from those who will be broadly served by the grant?	How will the target population be identified?	Unit of Analysis
Target population is Latino fathers who are low-income, 18+ years of age, have no open criminal cases (can be deferred), with children up to 24 years old	No difference, all program participants will be study participants.	The sample will be identified and recruited by community partner referrals and program staff.	Individual father

9.2. IMPACT EVALUATION ONLY: SAMPLE SIZE

If an impact evaluation is proposed, state the intended sample size (overall and by year), estimated attrition, and the anticipated size of the analytic sample (for both program/treatment and control/comparison groups). If the estimated analytic sample is expected to vary by outcome measure (e.g., outcomes measured using administrative records vs. survey data), you may copy the table below and label accordingly.

Year	Estimated Sample Size (# of individuals randomly assigned)		Estimated Size of Analytic Sample (# of individuals at analysis)	
	Treatment	Comparison	Treatment	Comparison
Year 1	N/A	N/A	N/A	N/A
Year 2	70	70	49	49
Year 3	162	162	113	113
Year 4	162	162	113	113
Year 5	50	50	35	35
TOTAL	443	443	310	310

9.3. RCTS ONLY: POWER ANALYSIS

For each confirmatory outcome, please provide power analyses demonstrating proposed sample sizes will be able to detect expected effect sizes for the outcomes targeted. Refer to previous studies of similar interventions for estimates of the required sample to inform power analyses. Note: If an impact evaluation is not proposed, this issue does not need to be addressed. You may use the table below to report the assumptions used in your power calculations, as well as the resulting minimum detectable impact for your confirmatory outcomes or provide them in the space below.

	Outcome 1	Outcome 2	Outcome 3	Outcome 4
Outcome Name	Healthier Parenting Attitudes	Healthier Partner Relationship Behavior	Healthier Parenting Behavior	Healthier Co-Parenting Behavior
Continuous or binary?	continuous	continuous	continuous	continuous

Level of significance (e.g., 0.05 percent)	0.05	0.05	0.05	0.05
Number of sides of test (one- or two-tailed)	One-tailed	One-tailed	One-tailed	One-tailed
Power (e.g., 80 percent)	80%	80%	80%	80%
Total number of individuals in analytic sample	620	620	620	620
If binary, enter mean of outcome variable				
If continuous outcome, enter the standard deviation of the outcome (>0)				
Proportion of individual-level (or within-group) variance explained by covariates				
For cluster RCTs: intraclass correlation coefficient	N/A	N/A	N/A	N/A
For cluster RCTs: proportion of group-level variance of	N/A	N/A	N/A	N/A

outcome explained by covariates				
Minimum detectable impact				
Minimum detectable effect size	0.2	0.2	0.2	0.2

If you did not provide report your assumptions using the table above, please enter them here.

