10.4. ENSURING AND MONITORING DATA COLLECTION

Describe plans for training data collectors and for updating or retraining data collectors about procedures. Detail plans to regularly review data that have been submitted and to assess and swiftly address problems.

This evaluation will utilize both post-program surveys (completed at the completion of core programming) and follow-up surveys collected six months after enrollment. The methods for these data collections differ. The primary driver for post-program survey completion is high rates of program retention. This data point will be collected during the last workshop session. As such, only those individuals who complete the program and who are at the data collection session will be likely to participate in the post-program data collection.

All program staff and evaluation staff will undergo a rigorous set of trainings to prepare for the evaluation. All staff receive an overview and introductory training to present the goals and objectives of the evaluation effort and its importance to the overall project. Next, all staff receive training on human subject protection and are required to pass a certification test on the subject matter. All staff will also receive a detailed training on the evaluation, including the evaluation tools, timing and data collection process, and the role and importance of randomization of participants.

In addition, the data manager and the primary local evaluation staff will undergo a rigorous training process to better understand the context of HMRF research, training on data collection procedures they will be responsible for, and training on the nFORM system and use of nFORM data in a CQI process. MER is creating networks of CQI data managers and Evaluation Project Managers across the 12 projects that we are evaluating so that all staff have access to experienced data managers and evaluation staff who have done this work previously. This training takes the form of weekly training sessions that are currently underway.

Members of the CQI team will also receive specific training on the MER CQI process that has been developed prior to the launch of data collection or program services. As described elsewhere, MER is assisting the program staff in implementing a robust CQI process that will focus on retention as one of the primary areas of program improvement, and as such, we are anticipating relatively modest levels of attrition for this data collection.

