TYRO Champion Dads

Statistical Analysis Plan

12/9/2024

Clinicaltrial.gov ID:
NCT05256992

1. Data Analysis

Briefly describe the planned approach for data analysis. If an impact analysis is proposed, name the key dependent and independent variables, and describe any methods to minimize Type I error (i.e., finding positive impacts by chance) such as limiting the number of impacts to be analyzed and/or multiple comparison correction. Describe proposed approach(es) for addressing missing data.

Identify impact study sample

The impact study sample includes participants who: 1) were eligible to be randomized based, 2) gave recorded informed consent to be part of the study and randomly assigned to a treatment group, and 3) took both an entrance and exit and/or follow-up survey. The CONSORT diagram in Appendix A shows exclusion criteria and the anticipated size of the overall impact study sample, which we anticipate to differ for attitudinal items that will use wave 2 data vs behavioral questions that will use wave 3 data. The analytic sample for particular outcome measures will vary based on missing data.

Defining analysis measures

For each outcome construct, we have identified the relevant measures from nFORM that are theoretically aligned with that construct. We will generate a correlation matrix between items in a given construct to ensure that theoretically related items are also empirically related in our data set. Items that are not strongly correlated with other items in a construct will be removed as necessary. Factor analysis will be used to ensure that all construct items hang together (using an alpha of 0.7 or higher as the threshold).

Once we are confident that all of the items align with a given construct, we will create a composite measure by taking an average of the scores on each non-missing item in the construct. The measure definition matrix below provides information on each proposed outcome measure.

For the sake of consistency and simplicity, parenting and co-parenting analyses will use a participant's youngest child as the focal child.

Measure	Sample	Variable Type	Data source(s)	Variable Name	Definition
Co-parenting relationship behaviors	Has at least one child age 24 or younger	Continuous (range from 1 to 5 where 1 is strongly disagree and 5 is strongly agree)	nFORM entrance, OLLE follow-up	Copar_Beh	Average of 11 survey items that relate to positive interactions with the mother of participant's youngest child

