Parenting relationship behaviors	Has at least one child age 24 or younger, saw child within past month	Continuous (range from 1 to 5 where 1 is never and 5 is every day or almost every day)	nFORM entrance, OLLE follow-up	Par_Beh	Average of 10 to 11 survey items (depending on child age) that relate to frequency of positive interactions with participant's youngest child
Parenting relationship attitudes	Has at least one child age 24 or younger, saw child within past month	Continuous (range from 1 to 5 where 1 is always and 5 is never)	nFORM entrance, nFORM exit	Par_Att	Average of 6 survey items that relate to frequency of feelings about participant's youngest child
Parenting relationship behaviors	Has at least one child age 24 or younger, saw child within past month	Continuous (range from 1 to 5 where 1 is never and 5 is every day or almost every day)	nFORM entrance, OLLE follow-up	Parent_Fight	Reported frequency of fighting with child
Partner relationship behaviors	All survey respondents	Continuous (range from 1 to 5 where 1 is never and 5 is always)	OLLE pre-survey, OLLE post-survey, OLLE follow-up	Partner_Fight	Reported frequency of fighting with partner
Partner relationship behaviors	All survey respondents	Continuous (range from 1 to 5 where 1 is never and 5 is always)	OLLE pre-survey, OLLE post-survey, OLLE follow-up	Partner_Disagree	Average of 7 survey items related to frequency of disagreement with partner on different topics

Analytic approach

The main goal of this impact study is to assess the impact of the addition of the Ray of Hope curriculum intervention on participant attitudinal outcomes immediately following program completion, and behavioral outcomes six months after program enrollment, as compared to the impact of standard TCD services alone.

Participation benefits are defined by the primary and secondary outcomes presented earlier in the theory of change logic model and with research questions and hypotheses. Impact estimates are based on participant responses to the OLLE Follow-up Survey across randomly assigned study groups to compare primary and secondary outcomes between them 6-months after TCD Project enrollment. More positive outcomes for the treatment group will be attributed to the intervention given that other TCD services are delivered in the same ways to both study groups under a shared condition.

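### The power table enters one analytic sample of 620 for all four outcomes, although the plan's own rules imply different samples; 620 has no reserve, so 80% power at 0.2 is not supported for each outcome

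*Protocol*

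**What the plan says.** Protocol 9.2 gives a single sample-size table: 443 randomised and 310 analysed per arm, which is 70% retention. Its template text allows a separate table where the analytic sample varies by outcome; none was made. Protocol 9.3 carries 310 + 310 forward. The row "Total number of individuals in analytic sample" reads 620 four times, and the row "Minimum detectable effect size" reads 0.2 four times, at one-tailed 0.05 and 80% power. The covariate R-squared row is blank.

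Other parts of the plan make the analysed sample depend on the outcome:

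- **Wave.** The SAP, under the impact study sample, refers to an anticipated overall size "which we anticipate to differ for attitudinal items that will use wave 2 data vs behavioral questions that will use wave 3 data". It adds that the sample for each measure will vary with missing data.
- **Subgroup.** The measure tables (Protocol 10.1 and the SAP) define the sample for the parenting attitude, parenting behaviour and child-fighting measures as "Has at least one child age 24 or younger, saw child within past month". The partner measures use all respondents. The co-parenting measure asks only for a child aged 24 or younger.
- **Missing items.** The SAP excludes a father from an outcome if more than 20% of the items of a composite, or a single-item measure, are missing. Outcomes are not imputed.
- **Exit survey.** Protocol 10.4 says that "only those individuals who complete the program and who are at the data collection session will be likely to participate" in the end-of-programme survey, which is the source of the attitude outcome.

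**The concern.** If the samples differ by wave, by contact with the child and by item completeness, one N is unlikely to be correct for all four outcomes. This would matter little if 620 left room to spare, but it is the number that just reaches 80% power at 0.2.

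The SAP names sufficient power as its means of controlling Type II error. A null result on parenting attitudes or parenting behaviour would then be read as if an effect of 0.2 had been detectable with 80% power, when the plan has not shown this for those outcomes.

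**Working it through.** **Inputs.** From Protocol 9.3: total N 620, alpha 0.05 one-tailed, power 80%, effect size 0.2 SD. From Protocol 9.2: 443 randomised and 310 analysed per arm. Allocation is 1:1. R-squared is taken as 0 because the cell is blank. Method: two-sample comparison of means, normal approximation, SD 1.

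**Step 1: reproduce the plan's figure.**

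- n per arm = 2 × ((1.645 + 0.842) / 0.2)² = 309.1, rounded up to 310, so 620 in total.
- Power at 310 per arm = Φ(0.2 × √(310/2) − 1.645) = Φ(0.845) = 80.1%.
- Minimum detectable effect = (1.645 + 0.842) × √(2/310) = 0.1997.
- Randomised per arm = 310 / 0.70 = 443.

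The table is correct on its own inputs. A two-sided test would need 393 per arm, so the one-tailed entry is the one that was used.

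**Step 2: which rules act on which outcome.**

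| Outcome | Survey wave | Sample rule | Exposed through |
|---|---|---|---|
| 1 Parenting attitudes | exit (wave 2) | contact with child in past month | wave response, contact rule, missing items |
| 2 Partner behaviour | six months (wave 3) | all respondents | wave response, missing items |
| 3 Parenting behaviour | six months (wave 3) | contact with child in past month | wave response, contact rule, missing items |
| 4 Co-parenting behaviour | six months (wave 3) | child aged 24 or younger, already an eligibility criterion | wave response, missing items |

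Outcomes 2 and 3 come from the same wave, but Outcome 3 carries an extra restriction. Unless every respondent had recent contact with the child, or missing items happen to offset the difference, their samples are not equal.

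**Step 3: what a shortfall costs.** The documents state no outcome-specific N, so the shortfall from 620 is an assumption, shown as a range. Power = Φ(0.2 × √(n/2) − 1.645) and minimum detectable effect = 2.487 × √(2/n), with n = N/2 per arm.

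| Shortfall (assumed) | N | Power at 0.2 | Minimum detectable effect |
|---|---|---|---|
| 0% | 620 | 80.1% | 0.200 |
| 5% | 589 | 78.3% | 0.205 |
| 10% | 558 | 76.3% | 0.211 |
| 20% | 496 | 72.0% | 0.223 |
| 30% | 434 | 67.0% | 0.239 |

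Power is more than two points below 80% once N is about 584 or lower, a shortfall of about 6%.

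**Step 4: what would keep 620 for a parenting outcome.** 620 / 886 = 70.0% of those randomised must be analysed. If 90, 80 or 70% of fathers meet the contact rule (illustrative shares; none is stated), survey response must be 70.0/0.90 = 78%, 70.0/0.80 = 87%, or 70.0/0.70 = about 100%, before any loss to missing items.

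**Step 5: what covariates could recover.** The minimum detectable effect scales with √((1 − R²)/N), so an R-squared equal to the lost fraction restores the original power. For example, a 20% loss with R-squared 0.20 gives 80.1%.

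**The case against.** The strongest reply is that no passage shows an N below 620 for any outcome. Protocol 9.2 labels the 310 per arm as individuals at analysis and does not say that the 30% loss is survey non-response alone, so the contact rule and item missingness may already be inside it. The SAP says that its Appendix A diagram shows the exclusions and the anticipated sample size; that diagram was not visible to us and may hold wave-specific numbers. The SAP gives no direction for the wave difference, so 620 could be the smaller wave. Protocol 10.3 allows the post-test during or after the last session, and 10.4 expects fairly modest attrition there. Covariates could offset a loss. The table reports the effect to one decimal, and every value in the range above rounds to 0.2.

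Much of this stands. A reader might infer that 80% power at 0.2 is not delivered, or that the table is wrong for every outcome. The documents do not support either reading: the loss is not quantified, the contact rule reaches only Outcomes 1 and 3, and the figure is correct at 620.

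The reply does not remove the conflict. Even if the 30% covers every kind of loss, a common 70% for outcomes with different waves and sample rules is at odds with the SAP's own expectation. The covariate gain cannot be assumed, because the R-squared cell is blank and the SAP adds only covariates that show a baseline difference. That one decimal hides a fall in power from 80% to 67% is a reason to report more decimals.

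**Conclusion.** The point holds as a conflict between the power table and the plan's own sample rules, not as an arithmetic error. The entry of 0.2 at 80% power is right for N = 620 and has no reserve below it. It is not supported for every outcome, and it is lost for any outcome analysed on fewer than 620 unless covariates compensate. Outcomes 1 and 3 are the most plausible cases. The partner and co-parenting outcomes are exposed only through wave response and missing items.

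If the shortfall is 5 to 30%, power at 0.2 is 78 to 67% and the minimum detectable effect is 0.205 to 0.239. These figures assume R-squared 0, equal arms and the table's one-tailed 0.05. They come before the Bonferroni correction that the SAP plans, which would lower power further and is a separate matter.

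**What to change.** In Protocol 9.2 and 9.3, replace the common 620 by an expected N for each outcome: number randomised × response at the relevant wave × share meeting the contact rule (Outcomes 1 and 3 only) × share with enough items answered. Say at which survey the contact rule is applied. Planned impact-study enrolment ended on 11-30-2024 and the SAP is dated 12/9/2024, so these rates can be taken from data already held, pooled over the arms and without comparing them. If Appendix A already gives wave-specific sizes, carry them into the table.

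State the assumed covariate R-squared and its source. Then give power at 0.2 and the minimum detectable effect, to at least two decimals, for each outcome.

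The cost is a revised table. No extra enrolment or change of analysis is needed, and the stated figures may become slightly less favourable.

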9.4. METHODS TO PROMOTE SUFFICIENT PROGRAM PARTICIPATION

Please describe methods to promote sufficient program participation in the table below.

What methods will you use to ensure sufficient sample is recruited, enrolls, and participates in the program?	Recruitment into TCD services and the study relies heavily on referrals from community partners who serve eligible parents. However, referrals also result from walk-ins to the ASF mini clinic, the ASF website that presents available services, advertising by ASF about the TCD Project, and word of mouth from TCD participants. Recruitment targets fathers but also accepts mothers who are: at least 18 years of age with no open criminal cases (can be deferred), largely low-income, interested in TCD services, and willing to be randomly assigned to either study group after informed consent.
Who will be responsible for recruiting the evaluation sample?	Case Managers under the supervision of the CQI Data Manager through community partnerships formed by [name], Project Director.
Please describe any incentives to be offered for program participation and/or completion and/or data collection and/or participation in the evaluation.	
Attendance Incentives:
 
 • \$25.00 e-gift card for attendance at workshops 1 – 3. • \$25.00 e-gift card for attendance at workshops 4 – 6 • \$25.00 e-gift card for attendance at workshops 7 – 9 • \$25.00 e-gift card for attendance at workshops 10 – 12 
Program completion incentives:
 
 • \$150.00 e-gift card for program completion plus TYRO Champion T-shirt, Champion Dad T-shirt, TYRO Pin and Certificate of Completion

• ASF also offers various wristbands displaying positive personal characteristics at various times based on participant engagement and group input.

Survey Completion Incentives:

- \$50.00 Giftogram gift card for OLLE Follow-up Survey

